5.7 Procedures for assessing HIV seroconversion

Presumptive HIV infections should be confirmed according to criteria developed by UK Standards for Microbiology Investigations. A repeat sample should be obtained and reactivity confirmed by a sensitive HIV RNA assay.

In the event of a seroconversion that presents to the prescribing clinic, information on adherence to PrEP will be elicited along with a sexual history as part of established clinical practice. In line with established clinical practice, collection of a sample for analysis of drug levels (therapeutic drug monitoring) may be considered.

In accordance with national guidelines for newly diagnosed individuals, a genotypic drug resistance test should be performed to identify mutations which may have been transmitted from the infecting partner or acquired as a result of exposure to PrEP. This test should be performed on the earliest possible sample after seroconversion.

5.8 Procedures for assessing safety

Information on serious suspected adverse drug reactions, including effects that are well recognised, should be reported by healthcare professionals at trial sites through the 'Yellow card' system (<https://yellowcard.mhra.gov.uk/>) in line with MHRA guidance of 23 January 2015 and subsequent updates. A copy of the yellow card form (whether completed online or by paper) should be retained in the investigator site file in all instances. Sites are expected to be able to provide these forms upon request from the Sponsor.

Any safety events raised via the 'Yellow Card' system will also be documented in the eCRF. At each visit, the clinic staff will be asked to enter if a yellow card has been raised for the participant. If yes, the following data is required to be entered into the database (this information is requested on the yellow card form and can be transcribed by sites):

- Suspected reaction
- Date of suspected reaction
- Outcome
- Severity
- If the suspected reaction is considered to have resulted from a medication error

Trial Oversight Committees will be provided with the data captured on the eCRF for safety monitoring purposes. If a committee raises any concerns with the data or requires a more comprehensive review, yellow card forms that have been retained in the investigator site file will be requested by the Sponsor.

Patient safety incidents that could have or did harm participants should also be reported through local incident reporting systems in line with routine clinical practice. Information on resistance mutations will be collected through the national HIV dataset.

5.9 Procedures for tracking patients across clinics

Patients often move between different sexual health services; we are anticipating that this could also occur within the context of this trial. Participants can be tracked across different clinics using their trial ID, which is assigned upon trial enrolment, but will not be able to be tracked via their GUMCAD number. GUMCAD numbers are allocated per patient and per clinic and therefore cannot be transferred across different services. In order to mitigate the risk of a participant enrolling twice, and hence taking two

places on the trial and affecting statistical analysis, patients will be asked to disclose that they are already on the trial if they move to a different clinic. This is stated in the participant information sheet and places importance of not double-enrolling on the trial from the perspective of denying another person access to PrEP. The participant's trial ID will be clearly documented on their copy of the completed informed consent form, which needs to be provided and verified when transferring to another clinic.

6 DEFINITION OF THE END OF THE TRIAL

The recruiting period is 33 months and the end of the trial is defined as 36 months from FPFV. Recruitment to the trial will be closely monitored by the Trial Steering Committee.

6.1 Treatment Compliance

The Chief Investigator will ensure that this trial is conducted according to the principles of the Declaration of Helsinki (1996) and meets all applicable regulatory expectations including, but not limited to, the Research Governance Framework, Research & Development policies and processes. In addition to this the sponsor will maintain oversight and quality management of this trial by undertaking regular monitoring activities and audits as appropriate.

6.2 Provision of treatment after the end of the trial

As the trial is non-interventional, post trial access to PrEP cannot be guaranteed to participants. PrEP is licensed for use in the UK and available to purchase privately, however it is currently unavailable on the NHS in England. All data generated from the trial will be presented to the TSC and provided to commissioners via the Oversight Board to inform future commissioning decisions on PrEP. The Board will seek to review the result of the research during the research period to minimise any gap in future commissioning and implementation decisions being taken. It is expected that the trial data will inform the commissioning of a PrEP programme to be implemented promptly on conclusion of the trial. Information will be shared with NHS England as commissioners of HIV drugs and local authorities as commissioners of sexual health services. It is anticipated that a national programme will be put in place with the expectation that PrEP will be available to all who are eligible, as informed by the data from this trial.

6.3 Early termination of the trial

The Funder, Sponsor or Chief Investigator may terminate either part of, or the entire trial for safety or administrative reasons. A written statement fully documenting the reasons for such a termination will be provided to the Ethics Committee and the Regulatory Authority as appropriate.

7 ADVERSE EVENTS

Information on serious suspected adverse drug reactions, including effects that are well recognised, will be reported through the 'Yellow card' system (<https://yellowcard.mhra.gov.uk/>). Patient safety incidents that could have or did harm participants should also be reported through local incident reporting systems in line with routine clinical practice. Any safety events raised via the 'Yellow Card' system will also be documented in the trial database.

Routine data will be collected on the presence of resistance mutations that are likely to have been selected by tenofovir disoproxil (K65R) or emtricitabine (M184V/I) or which preclude use of either drug in the treatment of HIV. See section 5.8 for procedures.

8 STATISTICAL CONSIDERATIONS AND DATA MANAGEMENT

8.1 Sample Size

The trial will recruit from the 'total' GUM clinic attending population in participating trial clinics. This is a subset of the 'total' GUM clinic attending population. A proportion of the attendees in participating GUM clinics will meet the trial eligibility criteria and of these the trial will recruit a total of 13,000 participants to receive PrEP. Estimates from GUMCAD 2016 suggested that the total eligible MSM population across all GUM clinics was approximately 10,000. The 10,000 target was considered sufficient to allow the size of the total eligible population (MSM and women and others) across all GUM clinics to be estimated with a precision within the range ± 480 to ± 1150 . These precision estimates were derived from a range of simulations using a number of assumptions derived from available GUMCAD data at the time. These include: the proportion of MSM meeting the eligibility criteria (estimated range 20% to 60%), the percentage of MSM at high risk (percentage with a bacterial STI in past year 25% to 55%), and percentage of non-MSM eligible (20% of the eligible MSM population).

Before the trial began and assuming that PrEP uptake in the eligible population lay within the range 20% to 60%, a trial size of 10,000 participants was deemed to be sufficient to estimate the precision for PrEP uptake within $\pm 3\%$.

Co-variables of major interest include clinic, clinical history of genital and rectal bacterial STI, geographical area of the country, age, and ethnicity. The possible combinations of these co-variables results in potential for large standard errors when considering sub group analysis.

Therefore, assuming that the smallest critical sub-group represents 5% of the trial population, the sample size of 10,000 provides a sufficiently narrow precision within each sub-group of 500 participants about the estimated numbers of eligible attendees (± 44 to ± 64) and the precision around the estimated proportion taking up the offer of PrEP of $\pm 6\%$.

The distribution, and the average duration of PrEP use are dependent upon the risk spectrum of the eligible population, and their duration of eligibility.

Based on the cumulative accrual of over 7,000 in the first 8 months of opening, mainly MSM, the Trial Management Group and independent Steering Committee, supported by the NIHR, have advised NHS England and the Association of the Directors of Public Health (ADsPH) that increasing the original sample size of 10,000 to 13,000 would provide useful additional data and address concerns about the representativeness of those who were recruited to the trial over the initial few months. A trial with 13,000 participants should be sufficient to enable the detection of meaningful differences in duration between sub-groups of participants. However, both the mean and variance of the duration of PrEP use is currently unknown. If there is substantial variance in the duration distribution then excessive differences may fail to be detected in small sub-groups.

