2. TRIAL OBJECTIVES

1. To measure PrEP-eligibility, PrEP-uptake, duration of PrEP-eligibility and duration of PrEP-use (PrEP prevention care continuum) among Genitourinary Medicine (GUM) clinic attendees,
2. To determine whether or not incident HIV infections in trial participants are due to non-adherence or biological failure,
3. To measure change over time in HIV diagnoses and incidence rate in those at high HIV risk,
4. To measure change over time in bacterial STI diagnoses and incidence rate in those at high HIV risk,
5. To measure the PrEP 'prevention care continuum' by clinic throughput and in different regions.

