8.3 Statistical Analysis

All analyses will be performed using STATA data analysis and statistical software version 13 or higher. Preliminary data review, analysis and presentation may be conducted throughout study duration at the request of the Trial Steering Committee. A detailed description of the analyses to be performed is outlined in the Statistical Analysis Plan (SAP). The analysis will address all outcomes of the trial and a descriptive baseline analysis will also be performed. Safety data will be extracted from 'yellow card' submissions.

To address the trial objectives, the following analyses will be undertaken:

- 1) PrEP eligibility: the total eligible population (numerator) will be estimated from the 'total' GUM attending clinic population (denominator). The clinic attending population will be categorised as 'eligible' or 'non-eligible' in participating clinics. Therefore, to estimate numbers eligible for PrEP among the 'total' GUM clinic attending population, a finite population correction will be used based on the total number of GUM clinics with post-hoc stratification weighting as necessary to account for observed differences between the sample and population with respect to important patient characteristics such as sexual orientation and age group.
- 2) Uptake of PrEP: The numerator is the population taking up an offer of PrEP, and denominator is the eligible population in participating GUM clinics. The uptake of PrEP will be estimated using a binomial generalised linear model with logarithmic link function, taking into account heterogeneity of clinics. An analysis of the predictors of PrEP uptake will be made, and will include time as a variable. There is a dynamic aspect to PrEP uptake (e.g. starting, stopping, restarting) which will be taken into consideration.
- 3) Duration of PrEP eligibility and use: Participants in the trial can be in one of three states: 'eligible for PrEP and on PrEP', 'eligible for PrEP but not on PrEP', and 'currently ineligible for PrEP'. Participants will move between these states. The analysis will use a multi-state model to estimate the

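### Section 8.1 gives one precision for every 5% sub-group, but for a small area made of whole clinics its own overall figures imply intervals about 2.2 to 4.0 times wider

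*Combined protocol and SAP*

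**What the plan says.** Section 8.1 gives two overall precisions for a trial of 10,000. The total eligible population is "to be estimated with a precision within the range" ±480 to ±1150, and 10,000 participants "was deemed to be sufficient to estimate the precision for PrEP uptake within" ±3%, for uptake anywhere from 20% to 60%. The figures for eligible numbers come from simulations. The between-clinic variance, the number of clinics and the confidence level are not given.

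The section then turns to sub-groups: "Co-variables of major interest include clinic, clinical history of genital and rectal bacterial STI, geographical area of the country, age, and ethnicity". It warns that combinations of these may have large standard errors. Then, "assuming that the smallest critical sub-group represents 5% of the trial population", it concludes that "the sample size of 10,000 provides a sufficiently narrow precision within each sub-group of 500 participants about the estimated numbers of eligible attendees". The values printed there are ±44 to ±64 for eligible numbers and ±6% for uptake. It draws no distinction between variables that cut across clinics (age, ethnicity, STI history) and those that are properties of whole clinics (area).

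Objective 5 in section 2 asks for the prevention care continuum "by clinic throughput and in different regions". Section 8.3 models uptake "taking into account heterogeneity of clinics". The later increase to 13,000 participants comes without a restated sub-group precision.

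**The concern.** An overall half-width of ±3% on 10,000 people is about three times the simple binomial value, so the overall figure already carries a large component beyond binomial error, most naturally variation between clinics. How that component passes to a sub-group depends on how many clinics the sub-group draws on. An age group found in most clinics averages over them almost as well as the whole trial does. An area holding 5% of the clinics averages over one twentieth as many. One printed precision cannot serve both.

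At stake is the planning claim behind the regional part of Objective 5. If 8.1 is read as written, a 5% area looks able to deliver ±6% uptake, and areas may be divided that finely for commissioning purposes when the design cannot separate them.

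**Working it through.** **Inputs, all from section 8.1:** overall ±3% uptake and ±480 to ±1150 eligible at 10,000; sub-group of 5% (500); printed sub-group values ±6% and ±44 to ±64; eligibility 20% to 60%. Assumed: 95% two-sided confidence (1.96), equal clinic sizes, and all excess over binomial error due to variation between clinics. The plan's simulations cannot be reproduced, because their between-clinic variance and number of clinics are not given. The between-clinic part is therefore solved back from the overall figures.

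**Step 1. What do the printed sub-group figures assume?**

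Uptake, at 50% (the widest binomial case):
- Binomial half-width: 1.96 × √(0.25/10,000) = 0.98%; for 500, 1.96 × √(0.25/500) = 4.38%.
- Between-clinic part overall: √(3² − 0.98²) = 2.84%.
- 500 spread over all clinics: √(2.84² + 4.38²) = ±5.2%.
- 500 spread over half the clinics: √(2 × 2.84² + 4.38²) = ±5.9%.

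The printed ±6% therefore fits a sub-group spread over about half the clinics or more.

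Eligible numbers, spread over all clinics:
- 20% eligible, from ±480: overall binomial 1.96 × √(10,000 × 0.8) = 175; between-clinic part √(480² − 175²) = 447, of which 5% is 22.3; sub-group binomial 1.96 × √(500 × 0.8) = 39.2; result √(22.3² + 39.2²) = ±45.
- 60% eligible, from ±1150: overall binomial 1.96 × √(10,000 × 0.4) = 124; between-clinic part 1,143, of which 5% is 57.2; sub-group binomial 1.96 × √(500 × 0.4) = 27.7; result ±63.5.

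These are close to the printed ±44 and ±64, but only with that pairing of 20% with the low end and 60% with the high end; a Poisson version gives ±49 to ±72. Over half the clinics they become √(2 × 22.3² + 39.2²) = ±50 and √(2 × 57.2² + 27.7²) = ±85, so the eligible figures need wider spread than the uptake figure does.

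**Step 2. A 5% sub-group made of whole clinics.** People per clinic stay the same and the number of clinics falls to one twentieth, so every variance component scales together.
- Uptake: 3% × √20 = ±13.4%; 13.4/6 = 2.2 times the printed value. A beta-binomial simulation with 100 and 200 clinics gave ±13.3% to ±13.6%.
- Eligible: 480 × √0.05 = ±107 and 1150 × √0.05 = ±257; 107/44 = 2.4 and 257/64 = 4.0 times.
- In reverse, ±6% for such an area needs an overall precision of 6/√20 = ±1.3%, and ±44 to ±64 needs 44 × √20 = ±197 to 64 × √20 = ±286.

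**Step 3. Where the gap ends, for uptake** (3% × √(1/share of clinics)):

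| Share of clinics | Half-width |
|---|---|
| 5% | ±13.4% |
| 10% | ±9.5% |
| 20% | ±6.7% |
| 25% | ±6.0% |
| one third | ±5.2% |

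**Step 4. Sensitivity.**
- If overall uptake precision is really ±2%: 2% × √20 = ±8.9%.
- If clinics within an area are more alike, with half the between-clinic variance: √(0.5 × 20 × 2.84² + 4.38²) = about ±10%. Reaching ±6% leaves room for only (36 − 4.38²)/(20 × 2.84²) = 0.10 of that variance.
- At 13,000: 3% × √(10/13) × √20 = ±11.8% if clinics rise in proportion, and at most ±13.4% if they do not.

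**The case against.** The inputs are inferred. Section 8.1 says uptake is estimated within ±3%, which may be a ceiling, and the eligible range may include extrapolation to clinics outside the trial. This stands: the exact factor is not established. But the overall figure would have to be ±1.3%, well inside the stated bound, before ±6% held for a 5% area.

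Section 8.3 defines uptake over the eligible population, whereas the 10,000 are people who took PrEP. This also stands, and it alters Step 1: with 10,000/0.5 = 20,000 eligible and 1,000 in the sub-group, the evenly spread value is about ±4.3%. It does not alter Step 2, because the √20 scaling does not depend on the denominator.

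Section 8.3 plans a finite population correction for eligibility. With equal sampling fractions it shrinks overall and area figures alike and cancels. It helps an area sampled much more completely than the country, which 8.1 does not describe.

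Section 8.1 also warns of large standard errors. That warning concerns combinations of variables, and the text goes on to call the precision for a sub-group of 500 sufficient.

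A reader might infer more than the documents support:
- *That throughput comparisons are two to four times too imprecise.* Section 3.1 names three levels; a stratum with about a third of the clinics and participants gives ±5.2% uptake.
- *That the same clustering problem affects single clinics.* Between-clinic variance does not enter the estimate for one named clinic, whose precision depends on its size (500 participants in one clinic would give ±4.4%).
- *That reported intervals will be too narrow.* Uptake is to be modelled allowing for clinic heterogeneity, so final intervals should reflect it. The fault lies in the planning claim.

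**Conclusion.** Section 8.1 contradicts itself for small whole-clinic sub-groups. For an area with 5% of the clinics, its overall figures imply about ±13% uptake and ±107 to ±257 eligible, against the printed ±6% and ±44 to ±64: 2.2 to 4.0 times wider. With about 600 eligible people in such an area (5% of 10,000 MSM plus the assumed 20% non-MSM), ±107 to ±257 is 18% to 43% of the estimate, where the printed figures suggest 7% to 11%.

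This rests on 95% confidence, ±3% being the actual overall precision, equal clinic sizes, and clinics in the area varying as much as all clinics. The documents do not give the number or size of the areas, so how many would fall near 5% is unknown. The direction is secure; the exact factor is not. For uptake, the printed value holds for whole-clinic strata with a quarter or more of the clinics and for sub-groups spread over about half the clinics or more.

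**What to change.** In 8.1, limit ±44 to ±64 and ±6% to sub-groups that cut across clinics: age, ethnicity and STI history. For areas and other strata made of whole clinics, state a separate, wider precision. Obtain it by re-running the original simulations at 13,000 participants, and report the number of clinics per stratum, the between-clinic variance, the confidence level, and whether a finite population correction is included. Until then the values in Steps 2 and 3 can serve as a guide; being back-solved, and from 10,000 rather than 13,000, they should not be printed as the plan's own precision.

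The cost is a re-run of existing simulations and a short rewording, with a less favourable stated figure for small areas. No extra participants are needed. How many areas to report, and whether to shrink single-clinic estimates, is the analysts' choice once the correct precision is known.

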8.2 Trial Outcomes

1. Proportion of Genitourinary Medicine (GUM) clinic attendees that meet PrEP eligibility criteria, the proportion that is prescribed PrEP per year and the duration of PrEP-eligibility and PrEP-use among users.

2. HIV and STIs:
 - a. HIV diagnoses in national dataset
 - b. STI diagnoses (gonorrhoea, chlamydia, syphilis and Hepatitis C) in national dataset
3. Adverse Events
 - a. Serious suspected adverse drug reactions reported using the yellow card system
 - b. Antiretroviral resistance associated mutations in participants with incident HIV infection

8.3 Statistical Analysis

All analyses will be performed using STATA data analysis and statistical software version 13 or higher. Preliminary data review, analysis and presentation may be conducted throughout study duration at the request of the Trial Steering Committee. A detailed description of the analyses to be performed is outlined in the Statistical Analysis Plan (SAP). The analysis will address all outcomes of the trial and a descriptive baseline analysis will also be performed. Safety data will be extracted from 'yellow card' submissions.

To address the trial objectives, the following analyses will be undertaken:

- 1) PrEP eligibility: the total eligible population (numerator) will be estimated from the 'total' GUM attending clinic population (denominator). The clinic attending population will be categorised as 'eligible' or 'non-eligible' in participating clinics. Therefore, to estimate numbers eligible for PrEP among the 'total' GUM clinic attending population, a finite population correction will be used based on the total number of GUM clinics with post-hoc stratification weighting as necessary to account for observed differences between the sample and population with respect to important patient characteristics such as sexual orientation and age group.
- 2) Uptake of PrEP: The numerator is the population taking up an offer of PrEP, and denominator is the eligible population in participating GUM clinics. The uptake of PrEP will be estimated using a binomial generalised linear model with logarithmic link function, taking into account heterogeneity of clinics. An analysis of the predictors of PrEP uptake will be made, and will include time as a variable. There is a dynamic aspect to PrEP uptake (e.g. starting, stopping, restarting) which will be taken into consideration.
- 3) Duration of PrEP eligibility and use: Participants in the trial can be in one of three states: 'eligible for PrEP and on PrEP', 'eligible for PrEP but not on PrEP', and 'currently ineligible for PrEP'. Participants will move between these states. The analysis will use a multi-state model to estimate the

probability of being in one of the states, the proportions in each state, the average duration in a given state, and transition between the states. A panel-data hazards model will be used to take into account difficulties with analysis such as between clinic variation, and the potential for more than one PrEP prescription per participant. A Gaussian random effect model will be used to enable between clinic variation to be modelled. The analysis will allow for subjects to drop out and re-enter the analysis dependent on eligibility status and will allow for multiple periods of PrEP use over time.

All analyses will include subject level covariates to assess differences between sub-groups. A time to event analysis will be used to estimate HIV incidence and will incorporate a 'cure fraction' model to take into account that the large majority of participants will not reach a HIV infection end-point. A mixed effects interrupted time-series analysis will be used to estimate the difference in the numbers of new HIV diagnoses between the pre-trial and during-trial periods in participating clinics. A time series analysis using conditional risk set model will be used to estimate STI incidence in those receiving PrEP due to the recurrent nature of STIs.

In addition, particular care will be required in the interpretation of the analyses due to the potential for risk spectrum¹ and health-seeking behaviour² biases. An outline of how these biases may be investigated and accounted for in the analyses is provided in the statistical analysis plan.

1. Risk Spectrum bias refers to the phenomenon that different clinics may have a different mix of patients in terms of risk. There may also be a difference in risk within clinics over time. For example, those participants who are enrolled into the trial early may report different levels of risk compared to those who are enrolled later on.

2. Health Seeking Behaviour bias refers to the phenomenon that participants coming forward to clinical services may be at different levels of risk compared to those who do not.

